a) What processes were devised to implement OPSS and why?

b) What processes were actually used to implement OPSS and how and why did they impact on initiation, embedding and integration?

c) What were the key factors influencing service delivery and acceptability?

d) What were people's experiences of providing an OPSS service?

Documents will be collected that pertain to the planned and actual implementation process including relevant local authority minutes, tender documents and annual service reviews.

Contextual observation that involves brief periods of work shadowing will be used with a smaller number of healthcare professionals and administrative staff (*max 3-5 per area*) to better understand

the actions and adaptation required to fit OPSS with work practices and their lived experiences of providing the OPSS journey. Handwritten field notes will record day-to-day work practices and information about online services and will be written up in narrative form. Contextual observations will comprise:

- (i) In person observation of healthcare professionals during clinical consultations
- (ii) Think aloud exercises about OPSS consultation scenarios with healthcare professionals (for example, with someone notified they are a contact of someone who has a STI; a routine screen; someone with symptoms or who will find out they have tested positive for chlamydia, HIV)
- (iii) Observation and think aloud exercises with administrative staff about managing clinical records and/or administrative tasks (the observer will position themselves so as not to see the clinical records or staff will use 'dummy records' to demonstrate processes)
- (iv) Observation of how information about online services features in the physical space of clinics (for example, how prominent it is and whether it is up to date).

The specific observations will be tailored to each clinic setting, in consultation with service professionals in each setting. Contextual observation will not include observation of patient identifiable data or remote consultations with service users.

Workstream 3 – Outcome

The outcome of this workstream will be an understanding of what services have done or would need to do for OPSS to be part of routine practice, including implications for patient flow and service model (e.g. to augment or replace clinic-based services), and an understanding of how implementation processes and service delivery models impact differentially on health inequalities and underserved or vulnerable populations.

Workstream 4 (Development of programme theories)

Workstream 4 runs alongside the other workstreams and brings together the data from each into a coherent whole. In other words, the focus of Workstream 4 is to ensure that the initial programme theories of impact and implementation of OPSS are iteratively refined into more detailed realist programme theories using relevant data from across all workstreams.

Workstream 4 – Design and methods

As is expected in any realist evaluation, at the start of the evaluation the initial programme theories will be developed (11) – one for the impact of OPSS and another related to its implementation. The initial programme theories will be developed by the project team drawing on the team's content expertise of the topic area and implementation (and especially normalisation process theory). They will set out how and why OPSS is thought to 'work' to generate the outcome(s) or impacts of interest. As mentioned above, our initial programme theory of implementation will be based on normalisation process theory. Our theories will be progressively refined over the course of the evaluation and 're-cast' in realist terms using relevant data drawn from all of the work streams. In other words, they will be developed such that they describe the contexts in which, populations for which, and main mechanisms by which, particular outcomes are, or are expected to be, achieved.

Workstream 4 - Data collection

Data to inform our interpretation of the relationships between contexts (C), mechanisms (M) and outcomes (O) will be sought across the different data sources from each workstream (e.g. mechanisms inferred from one source could help explain the way contexts influenced outcomes in a different source). Synthesising data from different sources is often necessary to compile CMO configurations, since not all parts of the configurations will always be found in the same source.

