Existing UK evidence on OPSS is often based on implementation in a single service (30–33), with the focus on assessing uptake rather than clinical (e.g. treatment, partner notification) outcomes. Data from a single centre shows OPSS can increase total testing activity, and that it is possible to shift simple STI testing online, freeing up clinic services for more complex cases (34). But initial evidence suggests OPSS is accessed by a higher proportion of people who are of white ethnicity (31,32,35), female and living in less deprived areas (32,35). Return rates for online STI tests vary (30,32,33,35) with non-return associated with being a heterosexual male, symptomatic, and living in more deprived areas (30).

Where OPSS treatment outcomes (e.g. proportion of people known to have received treatment) are reported, they are worryingly low, e.g. 46% (n=172/382) (31). Preliminary evidence suggests that time to treatment may be longer in those diagnosed online (31), increasing STI transmission potential. Virtually no data exist on partner notification outcomes (36), an intervention known to be more effective at reducing STI transmission than targeting wider populations for screening (37).

Costs and outcomes of OPSS services compared to clinic-based services are poorly understood (38–40). One US study provided evidence that an OPSS service could be cost-effective, but this was a small study based on modelled data (38). Online sexual health services also need to be considered as part of the changing sexual health economy and not simply as a 'bolt on' or standalone service (41).

Within the UK, the combination of poor treatment outcomes and potentially poor partner notification outcomes could have an adverse effect on clinical sequelae and transmission dynamics. This could therefore negatively impact public health outcomes and cost effectiveness of OPSS services. There are concerns that the most disadvantaged and vulnerable are likely to be most at risk of poor outcomes. Public Health England have highlighted 'a critical need to evaluate the impact of changes in service delivery on health inequalities...' (14).

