- Use of routinely collected data (e.g. National Sexual Health system and clinic datasets) within each case study area to determine the demographics and key clinical outcomes of people accessing OPSS services and clinic-based sexual health services, and how this has changed over time (2015-2022) (see example datasets, *Appendix 3*). The data will be examined to explore whether change differed between the areas, and whether change in clinical outcomes differed by population characteristics (reflecting a change in health inequality). Access to routinely collected data from national datasets requires Public Health England Office for Data Release approval, so this part of the study is described in a supplementary protocol v1.0 08.06.21.
- 2. Analyses of detailed behavioural and biological data within each case study area pre and post the implementation of OPSS services, including clinic and eService level, and data from large population surveys (e.g. British National Surveys of Sexual Attitudes and Lifestyles (www.natsal.ac.uk)). This will enable evaluation of triage/safe-guarding systems and impact on wider sexual health needs (e.g. HIV/STI prevention, vaccination, contraception). Population level data from outside sexual health settings will help contextualize health inequality and clinical findings.

Workstream 1.1 – Outcome measures

The primary outcomes are chlamydia, gonorrhoea, syphilis and HIV testing activity, chosen because they are important, captured by routinely collected data and sufficiently common to detect change over time. The analysis will determine whether the introduction of OPSS services is associated with overall changes in these activity measures and with differential change according to population characteristics (including age, gender, ethnicity, sexuality and Indices of Multiple Deprivation (IMD)), reflecting a change in health inequality.

Secondary outcome measures will capture the impact the introduction of OPSS has had on access to care, time to treatment, and other key public health and sexual health outcomes. These will include:

• Rates of new diagnoses of bacterial STIs and HIV

- Proportion of people diagnosed with chlamydia receiving treatment
- Proportion of people testing positive for gonorrhoea who receive appropriate treatment
- Proportion of people testing positive for gonorrhoea who have a test of cure
- Proportion of people with reactive tests who have confirmatory tests for HIV and syphilis

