- Partner notification rates for those diagnosed with chlamydia, gonorrhoea and HIV

For each of these outcomes, our analysis will explore whether change differs between the areas during the time-period being analysed, and whether change in clinical outcomes differ by population characteristics (including age, gender, ethnicity, sexuality and IMD).

Workstream 1.1 – Sample size

Three contrasting settings have been selected to serve as case studies. Our key objective which is most 'demanding' of the data, and hence drives the power calculation, is the detection of differences in the change in the primary outcomes after introduction of OPSS by key population characteristics. Data will be obtained over a continuous period before, during and after implementation of OPSS. However, to simplify the power calculation (and to be conservative) the comparison of one-year periods before and after OPSS are considered (different for each area).

As an example, analysis of data from one area is considered - Birmingham, and the testing rate for STIs excluding chlamydia for which data are publicly available. The rate changed from 193 per 1000 population in 2014 (pre OPSS) to 198 per 1000 in 2016 (post OPSS). With around 140,000 tests per year there is more than 99% power to detect a change as small as 1% in the proportion of those testing with a particular characteristic (e.g. ethnic minority group or gender) whatever the proportion before OPSS.

Workstream 1.1 – Data collection

Routinely collected data is captured by existing surveillance systems in England (e.g. Chlamydia Testing Activity Dataset, GUMCAD STI surveillance, HIV self-sampling dataset).

Data on clinical outcomes will be collected from routine information held by service providers in the case study areas. In each area, service user information is collected on electronic patient record systems and website databases. For each area, work will be undertaken to specify the fields to be included in the data extraction from service user records and website databases.

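### Treatment, test-of-cure, confirmation and partner-notification outcomes are all conditional on a group that OPSS can change, so a fall in a proportion cannot by itself distinguish more people treated from fewer

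*Protocol*

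**What the plan says.** Section 4, Workstream 1.1 – Outcome measures, makes testing activity the primary outcome. The secondary list opens with "Rates of new diagnoses of bacterial STIs and HIV", with no denominator stated, and then follows the care pathway:

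- For chlamydia, the treatment outcome is "Proportion of people diagnosed with chlamydia receiving treatment".
- For gonorrhoea there are two outcomes, appropriate treatment and test of cure, each taken as a share of those with a positive test.
- For HIV and syphilis, the outcome is confirmatory testing as a share of those whose test was reactive.
- Partner notification closes the list, worded as "Partner notification rates for those diagnosed with chlamydia, gonorrhoea and HIV".

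Each of these five is restricted to people diagnosed, positive or reactive. The protocol will examine whether change in each differs by area and by age, gender, ethnicity, sexuality and deprivation. Workstream 1.1 – Design and methods treats such a difference in clinical outcomes as a sign that health inequality has changed.

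Section 9 sets out Poisson models with a period-by-characteristic interaction, but for the primary outcomes. The rate per 1,000 population is given there for testing only, and is called informal because catchment sizes are estimates.

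Section 2 states "Data from a single centre shows OPSS can increase total testing activity". On treatment after OPSS diagnosis it says of reported figures that "they are worryingly low, e.g. 46% (n=172/382"), and it links poor treatment outcomes to possible adverse public health effects.

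**The concern.** The denominators of these outcomes lie downstream of the intervention. If OPSS raises testing, it may find infections that would otherwise have gone undiagnosed. If those people are treated less often than clinic patients were, the proportion treated falls even though each treated person is a gain. If instead OPSS replaces clinic diagnoses and treats them less often, the proportion also falls, and this time fewer people are treated. This holds even if the patients themselves are alike.

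The inequality question is the most exposed. Suppose one group gains extra OPSS diagnoses and another is unaffected. The interaction term on the proportion would go against the first group although more of its infections are being treated. Read alone, that could be taken as worse care or wider inequality when the population effect is the reverse.

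**Working it through.** **The plan's own figure.** 172/382 = 45.0%; the protocol prints 46%. The one-point difference does not matter here. The protocol's only power figure (above 99% for a 1% change with about 140,000 tests a year) concerns the make-up of those testing and has no bearing on these outcomes.

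**Inputs.**
- po, proportion treated after OPSS diagnosis: 172/382 (Section 2).
- pc, proportion treated in clinic: not in the protocol; assumed 70% to 95%.
- s, share of existing diagnoses that move online: assumed.
- e, added OPSS diagnoses as a share of baseline: assumed.

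**Formulas**, per 1,000 baseline diagnoses, with movers and added cases both treated at po:
- Treated after = 1,000 × [pc(1 − s) + po(s + e)]
- Proportion after = [pc(1 − s) + po(s + e)] / (1 + e)
- The number treated rises only if e·po > s(pc − po), that is, e/s > (pc − po)/po.

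**Results.**

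| pc | s | e | Proportion treated | Treated per 1,000 baseline diagnoses |
|---|---|---|---|---|
| 95% | 0 | 30% | 95% to 83.5% | 950 to 1,085 (+14.2%) |
| 90% | 0 | 20% | 90% to 82.5% | 900 to 990 (+10.0%) |
| 70% | 0 | 20% | 70% to 65.8% | 700 to 790 (+12.9%) |
| 90% | 20% | 10% | 90% to 77.7% | 900 to 855 (−5.0%) |
| 90% | 20% | 20% | 90% to 75.0% | 900 to 900 (no change) |
| 90% | 20% | 30% | 90% to 72.7% | 900 to 945 (+5.0%) |

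First row: (0.95 + 0.30 × 0.450)/1.30 = 1.085/1.30 = 83.5%. Fourth row: (0.90 × 0.80 + 0.450 × 0.30)/1.10 = 0.855/1.10 = 77.7%.

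In the last three rows the proportion is lowest where the most people are treated.

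**Break-even e/s** at po = 45.0%: 0.55 for pc = 70%, 0.78 for 80%, 1.00 for 90%, 1.11 for 95%.

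**Illustration with the protocol's Birmingham figures.** Section 4 gives testing of 193 per 1,000 before OPSS and 198 after: 198/193 = 1.026. Appendix 2 gives OPSS as 20% of activity. Assume diagnoses track both; this is rough, because the testing rate excludes chlamydia and the figures need not refer to the same year. Then OPSS diagnoses = 0.20 × 1.026 = 0.205 and clinic diagnoses = 0.821 of baseline. At pc = 95% and po = 45%, treated = 0.821 × 0.95 + 0.205 × 0.45 = 0.872, against 0.950 before: −8%. The proportion falls from 95% to 0.872/1.026 = 85%. Here both fall together.

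**The case against.** A reader might infer that the proportion and the number treated always move in opposite directions. They do so only if substitution is set to zero, in which case the result follows from the model. The protocol expects substitution: Sections 1 and 2 describe asymptomatic people being steered online while face-to-face services contract. On the Birmingham illustration the number treated falls in five of six combinations of clinic rate (90%, 95%) and OPSS rate (45%, 60%, 80%); only 90% with 80% shows a rise, of 0.3%. This objection stands. It makes the proportion ambiguous; it does not make it sufficient.

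A reader might also infer that the plan would report harm. It sets no such rule. The comment on low treatment is background on earlier evidence, and the protocol says only that differences in change will be explored.

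Nor are proportions the only information. Diagnosis rates are in the same, open-ended list, and rate times proportion gives an approximate yield. But that product is not planned, the rate has no stated denominator or breakdown by infection, and separate analyses of the two give no test of differential change in the yield. Confirmation is conditional on a reactive result, so its yield cannot be obtained from a diagnosis rate.

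Workstream 2 uses cost per patient treated and, if data allow, per partner identified or treated, so it needs counts. It is, however, a cross-sectional comparison of screening in asymptomatic people, and does not supply a before-and-after count by population group.

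Finally, an analysis plan may exist, and the national-data work has a supplementary protocol; neither is at hand and either may add counts. That limits the point to what this protocol fixes: its named outcomes and how differences in them are to be read.

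**Conclusion.** The concern holds in a limited form. The five pathway outcomes are valid measures of what happens to people once they have a result, but they cannot alone support a conclusion on public health effect or inequality, because OPSS can change who is in the denominator. In the scenarios above a falling proportion goes with anything from about 14% more people treated to about 8% fewer. The direction depends on whether added diagnoses relative to substituted ones exceed (pc − po)/po, which the protocol does not give.

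The sizes are illustrative. Only 172/382, the Birmingham testing rates and the 20% OPSS share come from the protocol; clinic treatment rates, added diagnoses and substitution are assumptions. The 172/382 counts people known to have been treated, so true treatment may be higher, which would shrink the effects. The ambiguity remains as long as OPSS treatment is below the clinic rate. The listed diagnosis rates address it only in part.

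**What to change.** Keep the proportions and describe them as measures of pathway quality. Beside each, add the matching number per period: people treated for chlamydia, people appropriately treated for gonorrhoea, people with a test of cure, people with a reactive HIV or syphilis result who had a confirmatory test, and partners notified. Also give each per 1,000 population, with the caveat on catchment estimates that Section 9 already applies to testing.

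Analyse these counts with the Poisson period-by-characteristic model planned for the primary outcomes. State in the outcome section that proportion, count and diagnosis rate are interpreted jointly before any conclusion on public health effect or inequality.

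The cost is modest. The person-level counts are numerators that the proportions already require, and the example local dataset in Appendix 3 lists treatment dates, confirmation results, partner outcomes and demographics. The drawbacks are a few more secondary outcomes, reliance on approximate catchment denominators, and London coverage, where detailed clinic data come mainly from two districts.

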I (investigator) agree to ensure that the confidential information contained in this document will not be used for any other purposes other than the evaluation or conduct of the research investigation without the prior written consent of the Sponsor.

I (investigator) agree to ensure that no research activity or recruitment will commence at participating research sites until the appropriate regulatory approvals and NHS confirmations of Capacity and Capability have been issued, and Sponsor green light confirmed.

I (investigator) also confirm that I will make the findings of the study publicly available through publication or other dissemination tools without any unnecessary delay and that an honest, accurate and transparent account of the study will be given. Any deviations from the study as planned in this protocol will be explained and reported accordingly.

Co-Chief Investigators:

Signature:

Date: 16/06/21

Print Name(in full): [name]

Position: Professor in HIV medicine / Honorary Consultant

Signature:

Date: 16/06/21

Print Name(in full): [name]

Position: Senior Clinical Research Associate / Honorary Consultant

On behalf of the Study Sponsor:

Signature: [name]

Date: 18/06/21

Print Name(in full): [name] Position: Research Governance Manager

STUDY SUMMARY

Identifiers					
IRAS Number	295506				
REC Reference No					
Sponsor Reference No	21/SC/0223 140431				
UCL Data Protection	140451				
Reference No	Z6364106/2021/04/36 health research				
Full (Scientific) title	Assessing the impact of introducing online postal self-sampling for sexually transmitted infections into sexual health provision within the UK on health inequalities, access to care and clinical outcomes				
Problem studied	To assess the impact of online postal self-sampling services on health inequalities, access to care, and clinical and economic outcomes, and to identify the factors that influence the implementation and sustainability of these services				
Study Type	Theoretically informed mixed-methods evaluation of three case study areas implementing online postal self-sampling services				
Target sample size	Up to 135 service users				
(qualitative research)	Up to 100 healthcare staff and other stakeholders				
Target sample size	>5,000 service users				
(quantitative research)					
STUDY TIMELINES					
Study Duration/length	39 months (including 3-month set	up phase)			
Expected Start Date	September 2021				

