9 DATA ANALYSIS

Workstream 1 (Impact evaluation)

Workstream 1.1 - Measurement of impact of OPSS on health inequalities, access, clinical and public health outcomes

For each case study area and primary outcome separately:

- Change will be analysed after introduction of OPSS in the overall number of tests and the proportion of those testing with particular population characteristics
- Change will be expressed in the rate of testing per year and, informally using estimates of the catchment area population size, change in the rate of testing per 1000 population per month, using Poisson regression and adjusting for population characteristics to address any possible confounding
- Change will be formally assessed in health inequality by testing for differential change over time (pre and post OPSS) by population characteristic (e.g. gender, ethnic minority group) through including interaction terms in the regression models
- Data will be pooled across the three areas to test for different change between areas

Analyses of Natsal-3 and Natsal-4 will provide estimates of the change over time in key outcomes within the general population, and insight into whether change is greater in areas that fully implemented OPSS services than others.

Our initial analysis is expected to be robust to confounding due to population change. To further address the possibility of confounding arising from other service changes that may have occurred at a similar time to OPSS, and the immediate impact of the COVID-19 pandemic, an analysis will be conducted based on an in-depth understanding of the health service provision over the full range of

time 2015-2022 in our case study areas. By collecting the dates of other changes in provision and pre-specifying the likely lag for these changes to affect our outcomes, Poisson regression models can be developed for our outcomes in continuous time that permit an 'interrupted time series' analysis to attempt to address the specific effect of OPSS adjusting for the effects of other changes.

Workstream 1.2 - Service user and healthcare professional experiences and views about acceptability of OPSS and clinic-based services

- 1. Quantitative data: The uptake of each component of the intervention will be analysed using logistic regression modelling for each component, stratifying by age, gender, sexuality, ethnicity, and IMD.

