23 APPENDICES

Appendix 1 – ASSIST study design

Appendix 2 – Case study areas

Birmingham and Solihull: The Umbrella service (https://umbrellahealth.co.uk/) was established in August 2015 as a new sexual health provider for Birmingham and Solihull serving a population of 1.3 million. It comprises a consortium of services which includes the NHS, local authorities and third sector. Each year Umbrella has over 110,000 patient contacts across nine clinic sites, via OPSS and through a network of 120 pharmacies. OPSS accounts for 20% of activity but this proportion is increasing year on year.

London: The London Sexual Health Programme is a unique collaboration, involving 30 London borough councils and the Corporation of the City of London. The programme introduced a new online sexual health service offering OPSS for STIs and HIV in January 2018 (https://www.shl.uk/). This service covers 28 of London's authorities, with an estimated population of over 7 million. London has the highest rate of STIs in England with 131,400 new STI diagnoses in 2016, 36% occurring in young people (aged 15-24) (47).

Sheffield: Sexual Health Sheffield (https://www.sexualhealthsheffield.nhs.uk) was contracted as the current model in November 2019, as Level 3 provider of sexual health for Sheffield, serving a population of 550,000. The service has over 50,000 contacts, face-to-face and via OPSS. OPSS accounts for 30% of activities.

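### The >99% power figure is correct for pooled non-chlamydia tests in Birmingham, but it does not describe the planned analyses of each infection in each area

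*Protocol*

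**What the plan says.** Protocol section 4, Workstream 1.1 – Sample size, names differential change in the primary outcomes by population characteristic as the most demanding objective and bases the power calculation on it. For simplicity, and as a conservative choice, "the comparison of one-year periods before and after OPSS are considered (different for each area"). The worked example is narrower: "analysis of data from one area is considered - Birmingham, and the testing rate for STIs excluding chlamydia for which data are publicly available". The result is "With around 140,000 tests per year there is more than 99% power to detect a change as small as 1% in the proportion", where the quantity meant is the share of testers who have a particular characteristic, with ethnic minority group and gender given as instances, and it is said to hold "whatever the proportion before OPSS".

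Workstream 1.1 – Outcome measures lists four primary outcomes: testing activity for chlamydia, gonorrhoea, syphilis and HIV. Section 9 opens the analysis with "For each case study area and primary outcome separately". It then covers both the number of tests and the proportion of those testing with a characteristic, and tests differential change through interaction terms.

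Appendix 2 gives a population of 1.3 million and over 110,000 contacts a year for Birmingham and Solihull. For Sheffield it gives a population of 550,000 and "The service has over 50,000 contacts, face-to-face and via OPSS". For London it gives over 7 million people. The study summary gives the quantitative target as ">5,000 service users".

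**The concern.** The power calculation is meant to support the inequality question, which the plan answers infection by infection and area by area. Its input is a count pooled over infections, from one area, without one of the four primary outcomes. Every test is also treated as an independent unit, although a person who tests twice brings the same sex and ethnicity each time. The wording nevertheless reads as a guarantee for any baseline.

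At stake is how a null interaction is read. If no differential change is found for one infection in one area, a reader relying on power above 99% could take that as firm evidence against a one-point shift when the data for that comparison are weaker.

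**Working it through.** **Inputs.** From the protocol: 140,000 tests per year, one year before against one year after, a change of 1%, any baseline, 193 tests per 1000 in 2014, and the Appendix 2 populations. Not stated and assumed here: two-sided 5% significance, independent units, and 1% meaning one percentage point.

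**Formula.** For n units per period and a proportion near 0.5 (the worst case), SE = √(2 × 0.25 / n) and power = Φ(0.01/SE − 1.96).

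1. **The protocol's own figure.** n = 140,000: SE = 0.00189, 0.01/SE = 5.29, power = Φ(3.33) = 99.96%. This is the minimum over all baselines. At a two-sided 1% level it is 99.67%. The statement reproduces.

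2. **Units needed for 99%.** n = (1.96 + 2.326)² × 0.5 / 0.01² ≈ 91,900 per year, for each infection in each area.

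3. **One infection in Birmingham.** If the 140,000 tests cover gonorrhoea, syphilis and HIV, at least one of them has at most 140,000/3 = 46,667 per year. Then SE = 0.00327, 0.01/SE = 3.06, power = Φ(1.10) = 86.3%. By baseline, power is 99.9% at 0.10, 96.6% at 0.20 and 91.3% at 0.30. It is below 99% from about 0.145 to 0.845. The minimum detectable change near 0.5 is 0.92 points at 80% power and 1.40 points at 99%. For the pooled count these are 0.53 and 0.81.

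4. **Chlamydia.** No test count is given, so nothing can be computed.

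5. **Sheffield (scaled; assumptions).**
   - Birmingham's rate: 0.193 × 550,000 = 106,150; divided by 3 = 35,383; power 75.8%.
   - Scaling the 140,000 by population: 140,000 × 550/1300 = 59,231; divided by 3 = 19,744; power 51.1%.
   - If the 50,000 contacts are annual and each gives one test for the infection in question: power 88.5%.
   - The first two differ because 140,000/0.193 ≈ 725,000, not 1.3 million. The protocol does not say which population the rate uses.

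6. **London (scaled; assumption).** 140,000 × 7/1.3, divided by 3, = about 251,000; power above 99.9%.

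7. **Repeat testing.** The pooled Birmingham claim falls below 99% once the design effect exceeds 140,000/91,858 = 1.52. No tests-per-person figure is given. The 140,000 tests set against about 110,000 contacts gives a ratio of 1.27, and 110,000 independent units would still give 99.7%.

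8. **Longer windows.** Two years each side at 46,667 gives 93,333 per period and 99.1%. Birmingham may not have two years before OPSS: the analysis period starts in 2015 and Appendix 2 dates the service to August 2015. If OPSS began then (assumption), about seven months precede it: 46,667 × 7/12 = 27,222. Against one year after, power is 74.6%. Against an unlimited later period, SE = √(0.25/27,222) = 0.00303 and power = Φ(3.30 − 1.96) ≈ 91%.

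**The case against.** The strongest reply is that nothing is miscalculated. The text calls this an example, uses one-year windows as a conservative simplification, and draws on routine data over several years that no recruitment target governs. Even after a three-way split, 80% power is reached for a change of just under one point, which is small. London passes easily. For Sheffield, three years each side at 35,383 would give 106,150 per period and 99.6% if tests were independent. People who test in both periods would offset part of the clustering loss. The national-dataset work also has a supplementary protocol, not available here, which may contain more.

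Much of this stands and limits the point. It does not remove it: this is the only power statement in the document, one-year windows are its stated basis, and window length addresses neither pooling over infections nor repeat testing.

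Four stronger readings are tempting and should not be drawn:

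- **The summary target contradicts the calculation.** ">5,000 service users" is an open-ended minimum that 140,000 satisfies. It is not tied to any area, period or infection, so it is uninformative but not in conflict.
- **1% is a relative change.** Power at 140,000 would then be 14% at a baseline of 0.10 and 75% at 0.50. That conflicts with the sentence's own claim to hold at every baseline, so the absolute reading is the coherent one.
- **The unit must be people.** Section 9 analyses numbers of tests as well as the make-up of those testing. The unit is undefined, not fixed.
- **Every planned comparison falls short.** London does not on this scaling, nor does Birmingham at baselines outside about 0.145 to 0.845 under the even split.

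**Conclusion.** The point holds as a mismatch between the power statement and the planned analysis, not as an arithmetic error. On the protocol's own one-year comparison, power above 99% at any baseline is shown only for a pooled Birmingham count without chlamydia. For at least one infection there, power is at most about 86% near a proportion of 0.5. For Sheffield it is about 76% if Birmingham's rate applied, with 51% to 88.5% across the scalings tried.

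These figures assume a two-sided 5% level, independent tests, and that the 140,000 are individual tests over three infections. If they instead counted screens that each covered all three, the split would not apply. The Sheffield and London figures are scaled, not documented. The design-effect limit of 1.52 is a threshold, not an estimate. Once infections are analysed separately, only repeat testing for the same infection contributes to it. The consequence is moderate: detectable changes stay small, but the assurance offered is stronger than the plan supports.

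**What to change.** Rewrite the Sample size paragraph in Workstream 1.1 to:

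- state the change as absolute percentage points, with the significance level and sidedness;
- say whether the unit is tests or people, in line with section 9;
- give expected annual numbers for each of the four infections, including chlamydia, in each area;
- apply an allowance for repeat testing, with its source or a range;
- replace the any-baseline claim with the resulting range of power, or with the minimum detectable change per infection and area, using the pre- and post-OPSS periods actually available.

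Optionally, link the summary's minimum number of service users to those expected numbers. The change is to wording and a short recalculation. It needs no extra data; the cost is a less favourable power statement, most visibly for Sheffield.
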